8.3.3 CLASSIFICATION OF AN ADVERSE EVENT

8.3.3.1 SEVERITY OF EVENT

For adverse events (AEs) not included in the protocol defined grading system, the following guidelines will be used to describe severity.

- **Mild** – Events require minimal or no treatment and do not interfere with the participant’s daily activities.
- **Moderate** – Events result in a low level of inconvenience or concern with the therapeutic measures. Moderate events may cause some interference with functioning.
- **Severe** – Events interrupt a participant’s usual daily activity and may require systemic drug therapy or other treatment. Severe events are usually potentially life-threatening or incapacitating. Of note, the term “severe” does not necessarily equate to “serious”.

8.3.3.2 RELATIONSHIP TO STUDY INTERVENTION/EXPERIMENTAL MANIPULATION

All adverse events (AEs) will have their relationship to study procedures, including the intervention, assessed by an appropriately-trained clinician based on temporal relationship and his/her clinical judgment. The degree of certainty about causality will be graded using the categories below.

- **Definitely/Probably Related** – There is evidence to suggest a causal relationship, and other possible contributing factors can be ruled out. The clinical event, including an abnormal laboratory test result, occurs in a plausible time relationship to study procedures administration and is unlikely to be explained by concurrent disease or other drugs or chemicals. The response to withdrawal of the study procedures should be clinically plausible. The event must be pharmacologically or phenomenologically definitive.
- **Potentially Related** – There is some evidence to suggest a causal relationship (e.g., the event occurred within a reasonable time after administration of study procedures). However, other factors may have contributed to the event (e.g., the participant’s clinical condition, other concomitant events). Although an AE may rate only as “possibly related” soon after discovery, it can be flagged as requiring more information and later be upgraded to “probably related” or “definitely related”, as appropriate.
- **Unlikely to be related/Not related** – A clinical event, including an abnormal laboratory test result, whose temporal relationship to study procedures administration makes a causal relationship improbable (e.g., the event did not occur within a reasonable time after administration of the study procedures) and in which other drugs or chemicals or underlying disease provides plausible explanations (e.g., the participant’s clinical condition, other concomitant treatments). Or, the AE is completely independent of study procedures administration.

8.3.3.3 EXPECTEDNESS

A clinician with appropriate expertise in treating youth anxiety and depression will be responsible for determining whether an adverse event (AE) is expected or unexpected. An AE will be considered unexpected if the nature, severity, or frequency of the event is not consistent with the risk information previously described for the study procedures, as outlined in this document, the consent materials and documents related to the video game and its use.

8.3.4 TIME PERIOD AND FREQUENCY FOR EVENT ASSESSMENT AND FOLLOW-UP

The occurrence of an adverse event (AE) or serious adverse event (SAE) may come to the attention of study personnel during study visits and interviews of a study participant presenting for medical care, or upon review by a study monitor.

All AEs, not otherwise precluded per the protocol, will be captured on the appropriate case report form (CRF). Information to be collected includes event description, time of onset, clinician's assessment of severity, relationship to study procedures (assessed only by those with the training and authority to make a decision), and time of resolution/stabilization of the event. All AEs occurring while on study will be documented appropriately regardless of relationship. All AEs will be followed to adequate resolution, such that the participant has been offered or received necessary care.

Any medical or psychiatric condition that is present at the time that the participant is screened will be considered as baseline and not reported as an AE. However, if the study participant's condition deteriorates at any time during the study, it will be recorded as an AE.

Changes in the severity of an AE will be documented to allow an assessment of the duration of the event at each level of severity to be performed. Documentation of onset and duration of each episode will be maintained for AEs characterized as intermittent.

A study team member will record events with start dates occurring any time after informed consent is obtained until 7 (for non-serious AEs) or 30 days (for SAEs) after the last day of study participation. At each study visit, the investigator will inquire about the occurrence of AE/SAEs since the last visit. Participants and/or their parent can spontaneously notify the investigator of an AE or health status change via phone call or email, if necessary, in between scheduled visits. Events will be followed for outcome information until resolution or stabilization.

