1.3 SCHEDULE OF ACTIVITIES

	Pre-screening (Pre-consent)	Assessment 1 Day 1	Assessment 2 Day 60±30	Assessment 3** 150±20
Review eligibility with phone screen	X			
Informed Consent		X		
Demographics		X		
Clinical assessment				
CBCL		X		
MASC		X	X	X
CDI		X*	X	X
K-SADS (Clinical report)		X		
SCARED-P		X		X
CDSRS		X*	X	X
C-SSRS		X		
ERQ-CA		X	X	X
Behavioral assessment				
Millisecond Inquisit Web Cognitive Battery		X	X	X***
Other assessments				
ESS			X	X
Adherence Metrics from Akili			X	X
Debrief				X
Adverse Events Reporting		X	X	X

*These assessments may be administered more than once if >14 days pass before the cognitive battery and cognitive training can be administered. See Section 6.4 for additional details.

**Assessment 3 was optional to participants and then discontinued in protocol version 2.1 (02 April 2024).

***Provided iPads will be re-collected after Assessment 2. If participants do not have access to a personal tablet from which they can complete the tasks from, then they will not complete the Cognitive Battery at Assessment 3 (if applicable).

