If the Parent study does not yield sufficient participation, then we will recruit through the community using the social media campaign strategies that have proven effective in our past work, including UMHealthResearch. The proposed study will add up to three additional timepoints of assessment (pre-intervention, post-intervention, and (if applicable) 3-months post-intervention. All study activities will be completely remotely via an encrypted HIPAA-compliant video conferencing platform (e.g., Zoom), phone

call, and/or Qualtrics links. Depressive symptoms, anxiety symptoms, general psychopathology, and cognitive control behavior as indexed by a *Millisecond Inquisit Web* Cognitive Battery will be assessed pre-intervention. After the intervention, the same symptoms and cognitive control behavioral will be assessed. These variables will optionally be assessed again 3-months post intervention.

Data analyses will compare pre- and post-CCT data. Additionally, multilevel models will assess change in depressive symptoms and cognitive control over time and comparing between those who received CBT as compared to those who received RMT in the Parent study. These data will include *Millisecond* measures of behavioral capacity for cognitive control and detailed assessment of depressive and anxiety symptoms using both clinician-interview and self-report. Pre- to post-CCT change in depressive symptom severity (clinician-measured) will serve as the primary outcome variable.

At protocol version 2.1 (02 April 2024), Assessment #3 (3-month follow-up) was removed to increase feasibility so that resources could focused on increased recruitment.

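### If participation ends at Assessment 2, now the last visit, the 7-day AE and 30-day SAE recording window in Section 8.3.4 contains no scheduled inquiry and relies on unsolicited reports

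*Combined protocol and SAP*

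**What the plan says.** Section 8.3.4 sets the recording period. It starts at informed consent and runs "until 7 (for non-serious AEs) or 30 days (for SAEs) after the last day of study participation". The same section gives the active method: "At each study visit, the investigator will inquire about the occurrence of AE/SAEs since the last visit". Section 8.3.5 repeats that participants are questioned about adverse events at each visit.

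Section 8.3.4 also gives a passive route: participants or parents "can spontaneously notify the investigator of an AE or health status change via phone call or email, if necessary, in between scheduled visits". For events already known, "Events will be followed for outcome information until resolution or stabilization". It adds that events may come to light when a participant presents for medical care or when a study monitor reviews the study.

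The Section 1.3 row "Adverse Events Reporting" is marked at Assessments 1, 2 and 3. Assessment 3 was optional and is now discontinued; Section 4.1 records that "Assessment #3 (3-month follow-up) was removed to increase feasibility". The schedule places the remaining post-intervention visit at "Assessment 2 Day 60±30". The documents do not say which day counts as the last day of participation.

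**The concern.** The plan states a recording period that extends beyond the final visit, but its only active means of learning about events is the visit. A period that nobody asks about can be reported as free of events simply because nobody was asked.

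The period matters here. Section 2.3.1 names worsening depressive symptoms, including emerging suicidality, as a risk of participation. Section 8.3.2 makes an inpatient hospitalisation an SAE. The study is fully remote (Section 4.1), and Parent study participants may live anywhere in the United States (Section 5.5), so a hospital admission need not come to the study team's notice. At stake is the completeness of the SAE count for that month. No efficacy estimate, test or power figure is affected.

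**Working it through.** No statistical formula applies. The check is day arithmetic on Section 1.3, followed by a count of the scheduled inquiries that fall inside the window.

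**Inputs**
- Window: 7 days (non-serious AEs) and 30 days (SAEs) after the last day of participation (Section 8.3.4).
- Assessment 2: Day 60 ± 30, so Days 30 to 90. Assessment 3, when it existed: Day 150 ± 20, so Days 130 to 170 (Section 1.3).
- Assumption for steps 1 to 3: the last day of participation is the last visit.

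**Step 1. Where the window ends**

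Window end = last visit day + 7 (AEs) or + 30 (SAEs).

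| Case | Last visit: earliest / nominal / latest | AE window ends | SAE window ends | Scheduled inquiries inside |
|---|---|---|---|---|
| Current plan | Day 30 / 60 / 90 | Day 37 / 67 / 97 | Day 60 / 90 / 120 | 0 |
| Before version 2.1, Assessment 3 declined | Day 30 / 60 / 90 | Day 37 / 67 / 97 | Day 60 / 90 / 120 | 0 |
| Before version 2.1, Assessment 3 attended | Day 130 / 150 / 170 | Day 137 / 157 / 177 | Day 160 / 180 / 200 | 0 |

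The count is zero in all three cases because the window is tied to the last visit, whichever visit that is.

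**Step 2. What Assessment 3 used to add**

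Interval from Assessment 2 to Assessment 3: shortest 130 − 90 = 40 days, nominal 150 − 60 = 90 days, longest 170 − 30 = 140 days. All exceed 30, so an attended Assessment 3 asked about the whole month after Assessment 2. That look-back has ended. The window after the final visit had no inquiry before the change and has none now.

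**Step 3. Whether another route asks the question**
- Spontaneous reports: described only for the time between scheduled visits, and no visit follows Assessment 2.
- Monitor review: Section 10.1.6 plans no regular external monitoring.
- Weekly Qualtrics checks (Section 10.1.7): no survey is scheduled after Assessment 2, and the same section ties well-being monitoring to the two assessments.
- iPad re-collection (Section 1.3) and payment (Section 5.5): both follow Assessment 2, but neither carries an AE question.

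**Step 4. Sensitivity to the undefined term**

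Suppose instead that the last day of participation is the last day of gameplay, and assume 28 days of training.
- Start on Day 1: last play is Day 1 + 27 = Day 28. Assessment 2 follows by 30 − 28 = 2, 60 − 28 = 32 or 90 − 28 = 62 days. At the nominal or latest date it covers the whole 30-day window; at the earliest it covers 2 days of it.
- Start on Day 14: last play is Day 14 + 27 = Day 41. At Day 60 Assessment 2 follows by 19 days, covering the 7-day window and 19 of the 30 days. At Day 90 it follows by 49 days and covers both. Day 30 would fall before training ended.

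So the gap ranges from the full window to none, depending on a definition that the plan does not give.

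**The case against.** The best reply is that Section 8.3.4 sets a rule for which known events count and does not promise active surveillance. A report by phone or email two weeks after Assessment 2 would be recorded, and nothing forbids it; treating the words about time between visits as closing that route is over-literal. This has force, and it is why the point is about reliance on unsolicited reports. It does not supply a question to families, and the plan describes no instruction to them to keep reporting for a further 30 days.

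A second reply is that the participants of most concern are already covered. Worsening or suicidality found at Assessment 2 leads to evaluation or referral (Sections 2.3.1 and 6.5.1), each participant is checked for worsening after the assessment (Section 10.1.7), and known events are followed to resolution. That stands. The gap concerns new events after Assessment 2 that nobody volunteers.

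A reader might also infer more than the documents support:
- **That version 2.1 caused the gap.** Step 1 gives zero inquiries before and after the change. The removal ended only the later look-back, and only for those who would have attended an optional visit.
- **That there is no contact after Assessment 2, or that the period is unobserved.** iPad return, payment, spontaneous reports and follow-up of known events all contradict this. The accurate description is no scheduled inquiry.
- **That the window's share of follow-up measures missed events.** For example, 30/(60 + 30) = 33% at the nominal date. This is a share of calendar time, depends on the undefined anchor day, and says nothing about how many events occur or go unreported.

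Finally, Section 9.4.4 gives safety analyses as not applicable, and no planned statement about events within 30 days appears anywhere. That limits the consequence to the completeness of recorded events.

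**Conclusion.** The concern holds in this form: taking Assessment 2 as the last day of participation, the 7-day and 30-day windows contain no scheduled AE or SAE inquiry, and capture depends on spontaneous reports in a remote study. The likely direction of error is an SAE count that is too low for that window.

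The documents give no event rate or reporting rate, so the number of missed events cannot be estimated. For scale only, with the initial target of 30 participants (Section 9.2), one participant whose SAE went unreported would be 1/30 = 3.3 percentage points of the crude proportion with an SAE.

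The conclusion rests on the anchor day. If it were the last day of gameplay, Assessment 2 could cover part or all of the window, as step 4 shows. This is a modest defect in safety ascertainment that is worth correcting.

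**What to change.** 1. In Section 8.3.4, define the last day of participation. The definition should also cover people who stop early: Section 5.5 says that those with under two weeks of training do not complete the post-intervention assessments, while Section 7.1 has remaining assessments go ahead where possible. These passages need to be reconciled.
2. Add one automated AE/SAE query to the parent, through the existing Qualtrics and email route, 30 days after that day. A single query then covers both the 7-day and the 30-day window.
3. List the query in the Section 1.3 schedule.

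The cost is one short survey link per family, which is a small burden. Existing staff would need some time to review responses and to assess severity and relationship for any event reported. No extra visit is needed.

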8.3.5 ADVERSE EVENT REPORTING

The occurrence of an AE may come to the attention of study personnel during study visits. At each visit, subjects will be questioned about putative AEs. Information to be collected includes event description, time of onset, clinician's assessment of severity (mild, moderate, or severe), relationship to study (assessed by the study PI and clinical team), expected versus unexpected, local versus systemic, and time of resolution/stabilization of the event. All AEs occurring while in the study will be documented appropriately regardless of relationship. All AEs will be followed to adequate resolution. Adverse event reporting will occur on the standard IRBMED timetable.

8.3.6 SERIOUS ADVERSE EVENT REPORTING

N/A

8.3.7 REPORTING EVENTS TO PARTICIPANTS

N/A

8.3.8 EVENTS OF SPECIAL INTEREST

N/A

8.3.9 REPORTING OF PREGNANCY

N/A

8.4 UNANTICIPATED PROBLEMS

8.4.1 DEFINITION OF UNANTICIPATED PROBLEMS

This protocol uses the definition of Unanticipated Problems as defined by the Office for Human Research Protections (OHRP). OHRP considers unanticipated problems involving risks to participants or others to include, in general, any incident, experience, or outcome that meets all of the following criteria:

- Unexpected in terms of nature, severity, or frequency given (a) the research procedures that are described in the protocol-related documents, such as the Institutional Review Board (IRB)-approved research protocol and informed consent document; and (b) the characteristics of the participant population being studied;
- Related or possibly related to participation in the research (“possibly related” means there is a reasonable possibility that the incident, experience, or outcome may have been caused by the procedures involved in the research); and
- Suggests that the research places participants or others at a greater risk of harm (including physical, psychological, economic, or social harm) than was previously known or recognized.

8.4.2 UNANTICIPATED PROBLEMS REPORTING

The investigator will report an other reportable incident or occurrence (ORIO) to the reviewing Institutional Review Board (IRB). The ORIO report will include the following information:

- Protocol identifying information: protocol title and number, PI’s name, and the IRB project number
- A detailed description of the event, incident, experience, or outcome
- An explanation of the basis for determining that the event, incident, experience, or outcome represents an ORIO
- A description of any changes to the protocol or other corrective actions that have been taken or are proposed in response to the ORIO

To satisfy the requirement for prompt reporting, UPs will be reported using the following timeline:

- ORIOs that are serious adverse events (SAEs) will be reported to the IRB and to the study sponsor/funding agency within 7 calendar days of the investigator becoming aware of the event
- Any other ORIO will be reported to the IRB within 7 calendar days of the investigator becoming aware of the problem

8.4.3 REPORTING UNANTICIPATED PROBLEMS TO PARTICIPANTS

N/A

9 STATISTICAL CONSIDERATIONS

9.1 STATISTICAL HYPOTHESES

Primary Endpoint:

We hypothesize that CCT will increase cognitive control capacity (Millisecond battery composite score and individual cognitive test scores) and reduce depressive symptoms (CDI and CDRS-R scores) over the 4 week period of the intervention. Specifically, we hypothesize that CCT will improve cognitive control which will in turn improve depressive symptoms as a consequence of enhanced emotional regulation. Alternatively, our null hypothesis is that there will be no difference in cognitive control capacity or depressive symptoms immediately post-intervention as compared to pre-intervention.

Secondary Endpoint*:

We hypothesize that CCT will further increase cognitive control capacity (measured by Millisecond battery composite score and individual cognitive test scores) and reduce depressive symptoms (as measured by CDI and CDRS-R) further 3-months post-intervention than immediately after the intervention. The null hypothesis is that there is no difference in cognitive control capacity or depressive symptoms from immediately post-intervention to 3-months after the intervention.

*Secondary endpoint was optional to participants and then discontinued after protocol version 2.1 (02 April 2024).

Feasibility/Acceptability and Experimental Endpoints:

1. We hypothesize that the majority of participants will complete the intervention with at least 80% compliance.
2. We hypothesize that participants will have favorable emotions associated with game play.
3. We hypothesize that depressive symptoms will be reduced from the baseline assessment of the Parent study but that they will be slightly elevated from the post-intervention assessment in the Parent study.

The statistical tests used to test these hypotheses will be outlined later in this protocol and registered with clinicaltrials.gov.

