1 PROTOCOL SUMMARY

1.1 SYNOPSIS

Title:	Cognitive Training Video Game to Target Subclinical Depressive Symptoms in Youth
Grant Number:	G028070
Study Description:	Youth with subclinical depressive symptoms (9-17) will be recruited to complete a cognitive training, video game-based, preventative intervention (CCT). Multilevel data (clinical measures of depression and anxiety symptoms and behavioral indexes of cognitive control capacity) will be collected before and after the intervention, to examine the extent to which CCT may reduce symptoms of depression and/or enhance cognitive control related behaviors.
Objectives:	
Primary Objective: To examine the efficacy of CCT in reducing depressive symptoms and improve cognitive control.
 
Secondary Objectives: To examine the durability of change in depressive symptoms and (if applicable) cognitive control 3-months after the CCT intervention.
 
Feasibility Objectives: 1) To assess whether participants engage in the intervention as instructed. 2) To assess whether participants enjoy engaging in the intervention. 3) To examine whether the effects of CBT in the Parent study have been maintained at a 2-year follow-up.

Endpoints:	
Primary Endpoints: Depressive symptoms and cognitive control behavioral performance after the intervention.
 
Secondary Endpoints: Depressive symptoms and cognitive control behavioral performance 3-months after the intervention. The secondary endpoint was discontinued as of protocol version 2.1 (02 April 2024).
 
Feasibility Endpoints: 1) Game-play metrics provided by Akili software; 2) ESS scores from each assessment; 3) Depressive symptoms at Assessment #1 of current study.

Study Population:	Anxious youth (AY) with subclinical depressive symptoms between the ages of 9 to 17.99
Phase or Stage:	N/A
Description of Sites/Facilities Enrolling Participants:	University of Michigan
Description of Study Intervention/Experimental Manipulation:	Participants will be recruited to complete the CCT intervention.
Study Duration:	Participants will be offered a 4-week, web-based cognitive control intervention (CCT), which is ~25 minutes a day x 5 days per week.
Participant Duration:	24 months
	Up to 6 months

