3 OBJECTIVES AND ENDPOINTS

OBJECTIVES	ENDPOINTS	JUSTIFICATION FOR ENDPOINTS	PUTATIVE MECHANISMS OF ACTION
Primary			
To examine the efficacy of CCT in reducing depressive and anxiety symptoms and improve cognitive control.	Depressive symptoms and cognitive control behavioral performance after the intervention.	We anticipate that CCT will result in increased cognitive control capacity, which will also relate to reductions in depressive symptoms.	Enhanced cognitive control ability (as trained with CCT) will improve the ability to regulate symptoms, thus lowering symptoms and reducing risk of developing full disorder.
Secondary*			
To examine the durability of change in depressive symptoms and cognitive control 3-months after the CCT intervention.	Depressive symptoms and cognitive control capacity 3-months post-intervention.	We anticipate that depressive symptoms will be reduced, and cognitive control enhanced, to a greater extent 3-months post-intervention as compared to immediately post-intervention.	Changes in cognitive control that may also support a reduction in depressive symptoms may have solidified over 3-months and therefore become detectable in self-report and clinician-administered assessments.
Feasibility/Acceptability and Experimental Outcomes			
1) To assess whether participants engage in the intervention as instructed.	1) Game-play metrics provided by Akili software; 2) ESS scores from	1) We anticipate that participants will play the game as instructed, 2) that they will have	Prior studies of EndeavorRx have demonstrated the feasibility and

OBJECTIVES	ENDPOINTS	JUSTIFICATION FOR ENDPOINTS	PUTATIVE MECHANISMS OF ACTION
2) To assess whether participants enjoy engaging in the intervention. 3) To examine whether the effects of CBT in the Parent study have been maintained at a 2-year follow-up.	each post-intervention assessment; 3) Depressive symptoms at Assessment #1 of current study	favorable emotions associated with game play and, 3) that depressive symptoms will still be reduced from the original baseline assessment, but that they will be greater than they were immediately after intervention in the Parent study.	acceptability of the intervention. Also, that treatment for anxiety disorders in the Parent study should also reduce co-morbid depressive symptoms, and that this reduction should be maintained over time.

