2. After completing one half of the CCT training (2 weeks), participants will *earn* an additional \$25.
3. Once the full training has been completed (4 weeks of at least 80% compliance), participants will *earn* another \$25.
4. *After completing Assessment #2, participants will *earn* another \$25.
5. **For those who have completed Assessment #3 3-months post-intervention, participants earn an additional \$25.

Therefore, if all three assessments are completed in addition to the full EndeavorRx intervention, each participant will receive a total of \$150. All participants will have the opportunity to earn the same amount of compensation (if completed Assessment #3). Incentives are structured to promote retention of participants throughout the full intervention period, as well as for Assessment #3 (if applicable). Payment for all enrolled participants will be made in up to two payments: at payment step #4* and again at payment step #5**, if all activities completed. If participants screen out during Assessment 1, they will be provided payment after screening out. The participant will receive the incentive directly. If a participant withdraws from the study or does not complete certain parts of the study, payment will be distributed for the amount earned at the point of study discontinuation. If a participant does not complete at least 2 weeks of the CCT intervention, they will not complete the post-intervention assessments.

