6.4 STUDY INTERVENTION/EXPERIMENTAL MANIPULATION ADHERENCE

Tolerability and compliance with the intervention will also be assessed. The CCT application will measure the amount of time each day that the child spends playing the video game. Additionally, completion of self-report questionnaires and *Millisecond* assessments will be tracked to ensure that these assessments are completed within the specified time period. If the cognitive task battery and start of the cognitive training intervention are not completed within sufficient time of the baseline clinical and self-report assessment (i.e., within 14 days of completing the CDI; due to scheduling and/or equipment constraints), then the CDI and CDRS-R will be re-administered prior to initiating the cognitive task battery and cognitive training.

Assessments will include (refer to 1.3 Schedule of Activities for a list of which measures are completed at each assessment):

Assessments by Clinician

- a) C-SRSS
- b) CDRS-R
- c) K-SADS

Assessments Completed by Subjects

- a) MASC
- b) CDI
- c) SCARED (parent)
- d) CBCL (parent)
- e) ERQ-CA

Other Assessments

- a) ESS (parent and child)

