- 9) Endeavor Satisfaction Survey (ESS; Subject, may be completed before and after CCT intervention) – A 5-item scale rating the participant's and participant guardian's feelings of satisfaction with the video game and its effect on participant's symptoms – approximately 1 minute.
- 10) Emotion Regulation Questionnaire for Children and Adolescents (ERQ-CA) – (Gullone & Taffe, 2012). A 10-item self-report questionnaire to assess emotion regulation (subcomponents of reappraisal and suppression) in children and adolescents. Approximately 5 minutes.

Electronic data capture:

Subjects will complete the self-report forms described above using Qualtrics. Qualtrics is an Application Service Provider (ASP) with a Software-as-a-Service (SaaS) platform for creating and distributing online surveys and related research services. The platform records response data, performs analysis, and reports on the data. All services are online and require no download software; only modern JavaScript-enabled browsers are required (no Java/JVM or Flash). Surveys are usually taken online within a web browser, with optional SMS surveys and offline methods available for smartphones/tablets. Qualtrics has been approved for the University of Michigan research community, and individual investigators access the web interface through a University of Michigan Qualtrics portal. Subjects will receive a coded link via email which will take them to the required surveys. The emailed link contains no identifiable information about the subjects, and once activated, establishes an https encrypted link with the Qualtrics server. Once completed, each survey is locked so that re-access is not permitted. We can also adapt the process for each subject, e.g. provide access on computers or tablets in the Department of Psychiatry for subjects who do wish or cannot use email. Some subjects may request paper, and, if so, paper forms will be provided.

Subjects will be asked to complete the consent form online (provided through a secure web-link sent via email) via SignNow prior to their initial evaluation. A copy of the consent will be emailed to the subject. Data will be downloaded from Qualtrics and stored on protected computers to be used for analysis.

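### The acceptability survey (ESS) is now scheduled only at Assessment 2, which early leavers may not reach, so acceptability is likely to be overstated if they liked the game less

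*Combined protocol and SAP*

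**What the plan says.** Whether participants enjoy the intervention is a named feasibility objective (1.1 and 3). Section 9.1 words the hypothesis as "We hypothesize that participants will have favorable emotions associated with game play". The endpoint in 1.1 is "ESS scores from each assessment", which the table in section 3 narrows to the post-intervention assessments. Section 8.1 describes the ESS as "A 5-item scale rating the participant's and participant guardian's feelings of satisfaction with the video game and its effect on participant's symptoms", and 6.4 lists it for both parent and child.

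- **Timing.** The schedule in 1.3 marks the ESS at Assessments 2 and 3 only. Assessment 3 was optional and was then discontinued at version 2.1, so Assessment 2 is what remains. Section 8.1 differs: "ESS; Subject, may be completed before and after CCT intervention".
- **Who reaches Assessment 2.** Section 5.5: "If a participant does not complete at least 2 weeks of the CCT intervention, they will not complete the post-intervention assessments". Section 7.1, by contrast, has a participant who gives up CCT but stays enrolled go through the rest of the study procedures. It also has outcome assessments go ahead for discontinued participants where this can be done.
- **Who is counted.** Under 7.2 the investigator may discontinue a participant for not engaging with the game, and anyone who received the intervention and then leaves is replaced. Section 9.3 defines a complete-case population at Assessment 2 and a per-protocol set with at least 80% compliance. Section 9.4.1 deletes cases with missing Assessment 1 or 2 data listwise.
- **Analysis.** Section 9.1 says that the tests for its hypotheses follow later, but nothing in 9.4 mentions the ESS. No favourable cut-off, rater or denominator is given.

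**The concern.** Dislike of the game is a natural reason to stop playing it. Taken together, these rules allow the least engaged participants to leave the acceptability result without trace. They may never be asked, they are replaced, and neither analysis set would include them.

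This is a single-arm pilot meant to inform larger studies (6.3, 9.2). Acceptability is one of the questions that such a design can answer well. A result that describes only those who stayed could lead the next study to plan for better engagement than it will get.

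There is also a smaller gap. The objective asks about participants' enjoyment, while the ESS is rated by parent and child and also covers perceived effect on symptoms. The plan does not say whose rating answers the hypothesis.

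**Working it through.** The plan gives no figure for this endpoint, so there is nothing of its own to reproduce. The 32 participants for 80% power in 9.2 relate to the planned analyses, among which the ESS does not appear.

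**Step 1: who can be missing.**

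| Participant | Is the ESS due at Assessment 2? |
|---|---|
| Stops CCT after at least 2 weeks, stays enrolled | Yes (7.1) |
| Stops CCT before 2 weeks, stays enrolled | No by 5.5, yes by 7.1: the sections conflict |
| Discontinued from the study after at least 2 weeks of CCT | Only where it can be done (7.1) |
| Withdraws or is lost before Assessment 2 | No ESS is scheduled at departure, so possibly none |

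**Step 2: the size, under assumptions.** Let k starters rate and m not rate, let p be the favourable share among raters, and let q be the share that would have been favourable among non-raters.

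- Share among all starters = (k·p + m·q) / (k + m)
- Overstatement = p minus this share = m·(p − q) / (k + m)

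Inputs: 30 starters is the recruitment target in 9.2. The value p = 80% is assumed, and so are q and m. The documents state no expected dropout. Two of the values for m echo the halting rule in 9.4.6, which mentions one third, or about 7 participants (one third of 30 is 10). That rule concerns withdrawal due to symptoms and is not a planned dropout rate. The results are expected shares, so the products need not be whole children.

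Example with m = 6 and q = 0: (24 × 0.80 + 6 × 0) / 30 = 19.2 / 30 = 64%, an overstatement of 16 points.

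| m of 30 not rating | q = 0 | q = 40% | q = 80% | Overstatement |
|---|---|---|---|---|
| 3 | 72% | 76% | 80% | 0 to 8 points |
| 6 | 64% | 72% | 80% | 0 to 16 points |
| 7 | 61% | 71% | 80% | 0 to 19 points |
| 10 | 53% | 67% | 80% | 0 to 27 points |

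**Step 3: with replacement, as in 7.2.** If non-raters are replaced until 30 have rated, then k = 30 and the number of starters is 30 + m. At q = 0 the share among all starters is 24/33 = 73%, 24/36 = 67%, 24/37 = 65% and 24/40 = 60% for m = 3, 6, 7 and 10. The gap is smaller for the same m, at about 7, 13, 15 and 20 points. The report would, however, show 30 ratings and no visible shortfall unless the number who started is also given. At q = 80% there is again no gap.

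**The case against.** A reader might infer that everyone who stops playing goes unrated. The documents do not support that. Under 7.1, those who stop CCT after at least 2 weeks but stay in the study are still due Assessment 2 and the ESS. The exposed group is those who stop before 2 weeks, and those who withdraw, are discontinued or are lost before Assessment 2.

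A reader might also take overstatement as established. It is not, because it requires non-raters to be less favourable than raters. Several routes out have no clear link to enjoyment: a medication change (5.3), new therapy (6.5), symptom worsening or hospitalisation (7.1), and loss of contact (7.3). If leavers felt as stayers did, the bias is zero.

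Nor do the documents show that parent and child ratings are pooled. Section 6.4 is compatible with separate forms. The items are not reproduced, so whether satisfaction can be split from symptom effect within five items is unknown.

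Finally, disengagement is seen elsewhere. Compliance is a separate feasibility hypothesis with automatic measurement, and reasons for leaving are recorded (7.1, 7.2). That is a fair point, and it softens the concern. But neither is an ESS score, and the plan does not bring either into the acceptability result. The possible pre-CCT rating in 8.1 does not help, since it would precede the play that is to be rated.

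**Conclusion.** The concern holds in limited form. As written, the plan schedules no rating from participants who leave before Assessment 2, replaces those who received the intervention, and defines no population of all who started. Acceptability is therefore likely to be overstated if those who leave early liked the game less.

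The direction is a reasoned expectation. The size is unknown, because the documents supply no dropout rate, ESS result or favourable cut-off. The range of 0 to 27 points rests on 30 starters, 3 to 10 of them not rating, 80% of raters favourable, and between none and 80% of non-raters favourable. Since 9.1 sets no threshold, no stated decision turns on it. This is a cheap improvement to a descriptive feasibility endpoint and does not threaten the primary analysis.

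Two inconsistencies need to be reconciled whatever else is done: 5.5 against 7.1 on assessment of those who stop before 2 weeks, and 1.3 against 8.1 on when the ESS is given.

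**What to change.** 1. Send the existing ESS link, child and parent, to everyone who started CCT. The trigger is recorded discontinuation of CCT, withdrawal, or the end of week 4, whichever comes first. Using a recorded event avoids having to define when a child has stopped playing.
2. Report child and parent ratings separately, and state in 9.4 that child ratings answer hypothesis 2. Fix the cut-off for a favourable rating before the data are examined.
3. Report the result among raters next to the number who started and did not rate, broken down by reason for leaving.
4. Add the share among all starters with non-responders counted as not favourable, labelled as a lower bound.
5. Reconcile 5.5 with 7.1, and 1.3 with 8.1.

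The cost is a changed trigger in the online survey already in use and a few lines in 1.3, 8.1 and 9.4, for a form that takes about 1 minute. No extra staff are needed. Some who quit will still not answer. The lower bound is conservative, because it counts departures unrelated to enjoyment as unfavourable, and for that reason it should not be presented as the estimate.
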